### **5.3.2 Secondary Efficacy Endpoints**

Secondary endpoints that will be assessed include:

- Urge to cough (UTC) 30 min and 90 min post last cough challenge
- Cough severity Visual Analog Scale (VAS) 30 and 90 min post last challenge.
- To evaluate changes in cough reflex sensitivity during acute cough associated with URTI in relation to the healthy (post-recovery) state

## **6.0 SAFETY ASSESSMENTS**

### **6.1 General Safety Assessments**

Safety was assessed through monitoring of adverse events/serious adverse events, physical examinations, vital signs, and 12-lead ECGs,

## **7.0 ANALYSIS POPULATION**

### **7.1 Full Analysis Set (FAS)**

All subjects who have taken at least 1 dose of study medication and provided at least 1 post-dose primary endpoint observation.

### **7.2 Per protocol set (PPS)**

All subjects who were fully compliant with the protocol completing all visits of the study.

### **7.3 Safety Set**

All subjects who have received at least 1 dose of study drug.

## **8.0 DEFINITION OF VARIABLES**

### **8.1 Baseline**

Unless otherwise stated, baseline is defined as the last observation recorded on or prior to the first study treatment.

## **8.2 Study Day**

Treatment phase 1b is the date of study medication.

## **8.3 Age**

Age will be derived as date of informed consent minus date of birth then divided by 365.25 and presented in years.

## **8.4 Prior and Concomitant Medications**

Prior medications are all those medications that are not concomitant (for which there is enough information to determine that the medication was stopped prior to the dose of study treatment). Concomitant medications are those medications that begin after the dose of study treatment or are present at baseline but continue after the dose of study treatment. Medications missing both start and stop dates or having a start date prior to the start of study treatment and missing stop date will be counted as concomitant medication.

## **9.0 GENERAL STATISTICAL CONSIDERATIONS**

Cough challenge analyses, cough frequency and urge to cough analysis and recovery will be conducted using SPSS (version.22) and Excel.

### **9.1 General Analysis Considerations**

For continuous variables, descriptive statistics will include the number of subjects reflected in the calculation (n), mean, standard deviation, median, minimum and maximum. categorical variables will be summarized using frequency counts and percentages.

Individual subject data obtained from the electronic case report forms (eCRFs), ECG data, cough challenge, and any derived data will be presented by subject in data listings to facilitate the investigation of tabulated values and to allow for the clinical review. In general, the disposition and demographics tables will be presented by time point sequence. All efficacy and safety tables will be presented by time point. In general, listings will be displayed by sorted unique subject identifier. A subject identification number is defined as a 3 digit sequentially assigned subject id number (xxx)..

The analyses described in this plan are considered a priori, in that they have been defined prior to database lock. Any analyses not described herein performed subsequent to database lock will be considered post hoc and exploratory.

## **9.2 Data Handling Rules for Cough Challenge Data**

For cough reflex sensitivity testing, if a subject didn't reach 5 or more coughs at a specific concentration of the challenge agent (i.e., missing C5), 1.5 times the maximum concentration level for the challenge agent will be imputed for the subject.

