### **Treatment Phase 1b**

Subjects who satisfied all entry criteria at baseline were then administered 20 mg ambroxol in the form of a lozenge, which was sucked until fully dissolved in the mouth.

The treatment was administered in the afternoon of the same visit day as the screening/baseline assessments.

The series of abbreviated cough challenges were conducted at 30 min and 90 min post dose.

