### **5.0 EFFICACY ASSESSMENTS**

#### **5.1 Cough Reflex Sensitivity**

Cough reflex sensitivity is measured by standard clinical methodology incorporating capsaicin, ATP, citric acid and distilled water cough challenges. The endpoints measured in cough challenge testing are concentrations of the challenge agents inducing 2 or more ( $C_2$ ) and 5 or more coughs ( $C_5$ ). In the case of distilled water the number of coughs generated in 1 minutes exposure will be recorded.

Cough challenges were carried out in accordance with the Study Site Standard Operating Procedures. Concentration range is pre-defined for each cough challenge agent and listed as below:

Distilled Water % Distilled Saline Control: 20%, 40%, 60%, 80%, 100%

Citric Acid Saline: 1 mM, 3 mM, 10 mM, 30 mM, 100 mM, 300 mM, 1M, 3M

Capsaicin Saline: 0.3  $\mu$ M, 1  $\mu$ M, 3  $\mu$ M, 10  $\mu$ M, 30  $\mu$ M, 100  $\mu$ M, 300  $\mu$ M, 1000  $\mu$ M

ATP Saline: 0.1 mM, 0.3 mM, 1 mM, 3 mM, 10 mM, 30 mM, 100 mM, 300 mM

Capsaicin, Citric Acid, ATP, and Distilled Water cough challenges will be administered 10 minutes apart and in a specific order for each subject (citric acid, capsaicin, ATP and distilled water) to determine  $C_2$  and  $C_5$ . Cough reflex sensitivity testing will be conducted at Baseline, at treatment phase 1b, 30 min and 90 min post dosing and at the Follow-up visit.

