## **5.3 Efficacy Endpoints**

### **5.3.1 Primary Efficacy Endpoints**

The co-primary endpoints are the average C2 and C5 across three time points (at baseline, 30 min, and 90 min post-dose) for capsaicin, ATP, citric acid and distilled water challenge: concentration inducing at least 2 coughs and at least 5 coughs. The primary endpoints include:

- Average C2 and C5 for capsaicin challenge
- Average C2 and C5 for ATP challenge
- Average C2 and C5 for citric acid challenge
- Average C2 and C5 for distilled water challenge

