### **10.5.1 Primary Endpoints**

Cough reflex sensitivity is measured by standard clinical methodology incorporating capsaicin, citric acid, ATP, and distilled water cough challenges. The standard end points measured in cough challenge testing are the concentrations of the challenge agents inducing 2 or more (C2) and 5 or more coughs (C5). In the case of distilled water the number of coughs generated in 30 seconds exposure will be recorded.

A natural log (LN) C2 and C5 is generally regarded as normally distributed within a population, so the treatment comparison will be performed using an ANOVA repeated measures model with Bonferroni corrected post hoc measurements. The ANOVA model will use all available data at 30 min and 90 min post dose with LN C2 and LNC5 as dependent variables and time points as independent variable.

The mean (in log scale) with the associated standard errors will be displayed which will be the average of C2 or C5 across three timepoints. Estimated differences from baseline along with corresponding 95% CIs and p-values will also be presented.

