### **10.5.2 Secondary Endpoints**

The secondary endpoints for subjects will be analysed using a one way ANOVA for repeated measures model with Bonferroni corrected post hoc measurements. The ANOVA model will use all available data at 30 min and 90 min post dose with Vas Scores as dependent variables and time points as independent variable.

The mean VAS scores with the associated standard errors will be displayed, Estimated differences from baseline along with corresponding 95% CIs and p-values will also be presented.

To analyse post-recovery change in C2 and C5, a mixed linear model will be performed with change from recovery in C2 and C5 concentration modeled as the response.

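### Section 9.2 says what to do when C5 is not reached but gives no rule for C2, a co-primary endpoint

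*SAP*

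**What the plan says.** SAP section 9.2 contains the only rule for a threshold that is not reached. It is triggered by failure to reach 5 coughs, which the text equates with a missing C5, and then "1.5 times the maximum concentration level for the challenge agent will be imputed for the subject".

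Section 5.3.1 gives C2 the same standing as C5: "The co-primary endpoints are the average C2 and C5 across three time points", for all four challenge agents. Section 10.5.1 takes LN C2 and LN C5 as dependent variables in an "ANOVA repeated measures model with Bonferroni corrected post hoc measurements" and adds: "The ANOVA model will use all available data at 30 min and 90 min post dose". For recovery, section 10.5.2 states that "a mixed linear model will be performed with change from recovery in" C2 and C5.

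Section 5.1 lists the concentrations, for example "Citric Acid Saline: 1 mM, 3 mM, 10 mM, 30 mM, 100 mM, 300 mM, 1M, 3M" and "ATP Saline: 0.1 mM, 0.3 mM, 1 mM, 3 mM, 10 mM, 30 mM, 100 mM, 300 mM".

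**The concern.** A subject who never reaches 2 coughs has not reached 5 either. As written, the C5 of that subject is filled in and the C2 stays empty. Such a blank is informative, because it occurs where cough sensitivity is lowest, and a drug that suppresses cough would produce more of them after dosing.

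The SAP does not settle what happens to the blank. A standard repeated-measures ANOVA needs all three time points and drops the whole subject. The wording on all available data suggests that only the empty value is lost. The two readings give different C2 results from the same data, and under either one C2 and C5 can rest on different subjects. Unless the site procedures settle the matter, the choice would be made with the data in hand, for one of two co-primary measures in a study of 14.

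**Working it through.** **Step 1: is the gap filled elsewhere?** Section 9.2 names C5 only. Sections 5.1, 5.3.1, 10.5.1 and 10.5.2 use C2 without a not-reached rule. Section 5.1 refers to site procedures, which are not shown. Within the SAP the gap stands.

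**Step 2: what the 1.5-fold rule means on the analysis scale.** The concentrations in section 5.1 rise 3- or 3.33-fold per step for citric acid, capsaicin and ATP.
- Increment from the rule: ln 1.5 = 0.405
- One ladder step: ln 3 = 1.099 or ln(10/3) = 1.204
- Ratio: 0.405/1.099 = 0.37; 0.405/1.204 = 0.34
- Distilled water: 1.5 × 100% = 150%, which cannot exist

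**Step 3: how much could the C2 gap matter?** The SAP gives no non-response rate, SD or effect, and section 9.3 offers no power calculation to reproduce. The following is an illustration on assumed inputs: capsaicin, n = 14, SD 1.2 between and 0.6 within subjects (LN), true rise 1.20 LN at 30 and 90 min, full concentration range also used after dosing. Latent thresholds are rounded up to the next concentration. Power is for 30 min versus baseline at 0.05/3 = 0.0167. There were 6000 simulated trials per setting, and 1500 for the all-available analysis (random-intercept model on observed values).

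Case A: median baseline C5 100 µM, C5 not reached in 4% at baseline and 20% after dosing. Case B, deliberately severe: median 300 µM, 18% and 50%. Cells show the C2 estimate (true value 1.20) and power.

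| Case; C2 below C5 by | C2 not reached post-dose | Subjects of 14 lacking a C2 | Whole subject dropped | Only the value dropped | 1.5× for C2 | Next step (3000 µM) for C2 |
|---|---|---|---|---|---|---|
| A; 0 | 20% | 3.9 | 1.13, 75% | 1.01, 82% | 1.03, 92% | 1.14, 95% |
| A; half a step | 10% | 2.1 | 1.16, 88% | 1.08, 92% | 1.12, 93% | 1.18, 95% |
| A; one step | 4% | 0.9 | 1.18, 93% | 1.16, 96% | 1.16, 95% | 1.19, 96% |
| B; 0 | 50% | 8.4 | 1.05, 33% | 0.75, 38% | 0.74, 79% | 0.96, 90% |
| B; half a step | 33% | 5.9 | 1.10, 58% | 0.90, 66% | 0.91, 88% | 1.08, 93% |
| B; one step | 18% | 3.5 | 1.14, 78% | 1.02, 84% | 1.05, 93% | 1.15, 95% |

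**Step 4: settings where little is lost.** Same SDs and rise, whole subject dropped versus next step:
- Median C5 30 µM, C2 equal to C5: 0.9 of 14 affected; power 93% v 96%
- Median C5 30 µM, C2 half a step lower: 0.3 affected; 95% v 96%
- Median C5 100 µM, C2 two steps lower: 0.1 affected; about 96% for both
- Median C5 300 µM, C2 two steps lower: 0.8 affected; 94% v 95–96%

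**Step 5: false positives.** With no true change, each rule stays near nominal: 1.2–1.9% per comparison (nominal 1.67%) and 3.3–5.0% for the overall F test.

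**The case against.** The strongest reply is about weight. C2 needs fewer coughs than C5, so fewer subjects miss it, and the large losses appear only when the two thresholds nearly coincide and many subjects are off the range. That stands: step 4 shows the loss almost vanishing elsewhere. A reader might take 33% against 90% power as the likely cost. The documents do not support that, because they give no ceiling rate. The illustration also uses the full range after dosing, whereas the SAP says: "The series of abbreviated cough challenges were conducted at 30 min and 90 min post dose". Its sizes may not describe this trial.

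Second, the SAP has partial safeguards. Section 9.1 requires n in the summaries and listings by subject, so blanks would be visible, and it labels undescribed analyses done after database lock as exploratory. The study is itself exploratory. This lowers the stakes but does not supply the rule.

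Third, a reader might infer from step 2 that the 1.5-fold value is itself wrong, must be replaced by the next ladder step and must not be extended to C2. That goes too far. Both are single imputed values. The 1.5-fold rule is prespecified and causes no false positives. For C5 its power is 92% against 95% for the next step in case A, and 79% against 90% in case B. Extended to C2 in case A it gives 92–95% power. Nor does the next step make C2 and C5 agree: in case B it gives 0.96 for C5 and 1.15 for C2 one step lower.

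**Conclusion.** The concern holds as a gap in a prespecified rule: section 9.2 covers C5 and leaves its co-primary partner C2 without a rule, so followed literally the plan loses C2 values where sensitivity is lowest. This is certain from the text of the SAP, unless the unseen site procedures supply a rule.

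The size is not known. On the assumed inputs, the power given up by dropping whole subjects instead of extending the 1.5-fold rule ranges from practically nothing to 79% − 33% = 46 percentage points, the latter only in the most severe setting. If every subject reaches 2 coughs at every time point, nothing changes. The documents do not show that the trial's result is biased, and there is no false-positive inflation. The point should be fixed because the remedy is cheap, not because harm has been shown.

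**What to change.** Amend section 9.2 so that the same not-reached rule applies to C2 and C5 at baseline, 30 min, 90 min and follow-up for citric acid, capsaicin and ATP. Extending the present 1.5-fold rule to C2 closes the gap. Report the number of thresholds not reached by agent, endpoint and time point.

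Do not apply the rule to distilled water. First reconcile whether its endpoint is C2 and C5 (section 5.3.1) or a cough count (sections 5.1 and 10.5.1).

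Optionally, because 1.5-fold adds about a third of a ladder step, add a sensitivity analysis that uses the next step above the maximum, as an analysis value only.

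The cost is one or two sentences and one table, within the planned SPSS and Excel analysis. The drawback is that a single imputed value is treated as exact and shrinks the estimate when many subjects are off the range. In case B with C2 equal to C5, the 1.5-fold estimate of 0.74 is further from 1.20 than the 1.05 from dropping subjects. What is gained there is that all 14 subjects are kept instead of 14 − 8.4 = 5.6, with C2 and C5 resting on the same subjects.

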## **9.3 Determination of Sample Size**

Because the effects of ambroxol on these challenge solutions are currently unknown it is impossible to provide an accurate power calculation. However, previous studies done in subjects with acute cough have demonstrated a significant change in C2 and C5 using 14 subjects. Since these are essentially experimental studies rather than trials of drug efficacy, studies of smaller effects, requiring a larger number of subjects are inappropriate and would not support the hypotheses being tested.

## **10.0 STATISTICAL ANALYSES**

### **10.1 Subject Disposition**

The number and percentage of subjects who completed the study and the number and percentage of subjects who were withdrawn will be presented. Subjects who discontinued prematurely will be summarized by number and percentage by reason for discontinuation (subject withdrew consent, adverse event, lost to follow-up, non-compliance, study terminated by sponsor, other).

Protocol deviations will be listed and may be summarized.

### **10.2 Eligibility Assessments**

Subject's eligibility assessments will be listed.

#### **10.3.1 Demographic and Baseline Characteristics**

Demographic and baseline characteristics will be listed. Variables include gender, age, and race.

#### **10.3.2 Medical History**

Medical history will be listed.

#### **10.3.3 Screening Laboratory Tests**

Pregnancy tests data will be listed.

#### 10.4 Prior and Concomitant Medication

Prior and concomitant medications will be coded to anatomical therapeutic class and preferred name using the WHO drug dictionary. Listings and tabular summary of prior and concomitant medications will be presented by subject health status (health or chronic cough) at baseline. All medications will be classified using the Anatomical Therapeutic Chemical (ATC) classification codes and preferred drug names from the World Health Organization Drug Dictionary (WHO-DD), Q1March2014.

For the medications recorded on CRF page “Prior and Concomitant Medications”, medications with a stop date before the date of study drug will be considered prior medications. Medications with start date or stop date on or after the first date of study drug dosing will be considered concomitant medications.

Prior medications and concomitant medications will be presented in tabular form using the ATC Level 2 (pharmacological subgroup) and preferred term (PT). Frequencies and percentages will be presented. The counts of medications will also be summarized. The tables will be sorted by overall descending frequency of ATC Level 2, and then, within an ATC Level, by overall descending frequency of PT. If a concomitant medication has a start date prior to dosing date (Day 1) and continues over the study, will be considered as concomitant medications to be summarized in a separate table from the other concomitant medications with start date on or after dosing.

##### Partial or Missing Medication Start and Stop Dates

If the medication start date is incomplete, then it will be imputed as follows for the purpose of determining concomitance only:

- If the start date is completely missing, the start date will be equal to the dose date. However, if the stop date is not missing and is before the dose date, then the stop date will be used instead.
- If the start day is missing, the first day of the month will be used.
- If the start day and month are missing, then the first day of the first month (January) will be used.

If the medication stop date is partial, then it will be imputed as follows for the purpose of determining concomitance only:

- If the stop date is completely missing and the medication is not ongoing, the stop date will be equal to the dose date or date of completion/withdrawal, whichever is the latest.

- If the stop day is missing, the last day of the month will be used.
- If the stop day and month are missing, then the last day of the last month (December) will be used.

The aforementioned missing or partial data handling rules will be applied to the summary tables. The recorded missing or partial date values will be presented in the listings.

## **10.5 Efficacy Analyses**

All efficacy analyses will be based on FAS set.

### **10.5.1 Primary Endpoints**

Cough reflex sensitivity is measured by standard clinical methodology incorporating capsaicin, citric acid, ATP, and distilled water cough challenges. The standard end points measured in cough challenge testing are the concentrations of the challenge agents inducing 2 or more (C2) and 5 or more coughs (C5). In the case of distilled water the number of coughs generated in 30 seconds exposure will be recorded.

A natural log (LN) C2 and C5 is generally regarded as normally distributed within a population, so the treatment comparison will be performed using an ANOVA repeated measures model with Bonferroni corrected post hoc measurements. The ANOVA model will use all available data at 30 min and 90 min post dose with LN C2 and LNC5 as dependent variables and time points as independent variable.

The mean (in log scale) with the associated standard errors will be displayed which will be the average of C2 or C5 across three timepoints. Estimated differences from baseline along with corresponding 95% CIs and p-values will also be presented.

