## 3.0 STUDY DESIGN AND PROCEDURES

This was an open label, single centre exploratory study in patients with acute cough related to respiratory tract infection.

There was a Screening/Baseline and combined Treatment visit. Subjects return approximately 1-4 weeks after their treatment once all symptoms had subsided and the subject was no longer suffering from URTI, for a Follow-up Visit.

14 subjects with acute cough in relation to a URTI and who meet all entry criteria were be assigned to:

**Treatment** p.o 20mg ambroxol lozenge  
(Lysopain Ambr MintM)

At the Screening Visit/Baseline Visits and during Treatment phase, cough sensitivity (Section 5.1) was measured by standard clinical methodology incorporating four cough challenges (capsaicin, ATP, citric acid and distilled water).

Refer to the Schedule of Assessments and Procedures located at the end of the SAP (Appendix A) for additional details. The study includes the following study periods and scheduled visits:

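### SAP 10.5.1 and 10.5.2 do not state the Bonferroni family over time points: name the two baseline contrasts and test them with Holm, so that no alpha can go to the unreported 30 v 90 min pair

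*SAP*

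**What the plan says.** SAP 5.3.1 defines the primary endpoints "across three time points (at baseline, 30 min, and 90 min post-dose", so the time factor has three levels. SAP 10.5.1 compares them "using an ANOVA repeated measures model with Bonferroni corrected post hoc measurements" and adds: "Estimated differences from baseline along with corresponding 95% CIs and p-values will also be presented". For the VAS scores, 10.5.2 plans a "one way ANOVA for repeated measures model with Bonferroni corrected post hoc measurements" and also promises differences from baseline with 95% intervals and p-values.

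The SAP leaves four things open:
- how many comparisons the Bonferroni correction covers;
- the alpha level and whether tests are two-sided;
- whether the 95% intervals are adjusted;
- whether baseline is a level of the model. The model sentence reads "The ANOVA model will use all available data at 30 min and 90 min post dose" and does not mention baseline, although the reported differences need it.

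Neither section lists a 30 v 90 min comparison, and none of the objectives in 2.1 and 2.2 asks for one.

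**The concern.** A three-level factor has three pairwise comparisons. Bonferroni described as post hoc is commonly run over all of them, which puts each test at 0.05/3 = 0.0167. Only two of the three answer a question the SAP asks. On that reading, the two reported comparisons are tested more strictly than a 5% bound on their familywise error requires. The study has 14 subjects, and SAP 9.3 rules out enlarging it to find smaller effects, so the efficiency of the analysis counts.

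The open family matters in itself. Two analysts following the same text could use 0.0167 or 0.025 per test. A 95% interval without a stated adjustment may also sit beside an adjusted p-value and differ from it on significance.

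**Working it through.** **Inputs.** From SAP 3.0: "14 subjects with acute cough in relation to a URTI", one arm, within-subject comparison. Levels and contrasts are as set out above. Alpha is assumed to be 5% two-sided, in line with the 95% intervals. There is no power figure in the SAP to reproduce: 9.3 offers no calculation, "Because the effects of ambroxol on these challenge solutions are currently unknown". The effect sizes and correlations below are therefore assumptions. dz is the mean change from baseline on the log scale divided by the SD of that change, and r is the correlation between the 30 min and 90 min changes.

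**Critical values (paired t, 13 df).** 2.746 at 0.05/3 = 0.0167; 2.533 at 0.05/2 = 0.025; 2.160 at 0.05. Holm over two contrasts tests the smaller p-value at 0.025 and, if that succeeds, the larger at 0.05.

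**Power of one contrast.** Power = P(|T| > critical value), where T is noncentral t on 13 df with noncentrality dz × √14. For dz = 0.8 this is 0.8 × 3.742 = 2.99. The single-step columns are exact. The Holm column is simulated (200,000 trials, both contrasts at the same dz, r = 0.5).

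| dz | Bonferroni, 3 pairs | Bonferroni, 2 contrasts | Holm, 2 contrasts |
|---|---|---|---|
| 0.5 | 23.4% | 29.2% | 33.3% |
| 0.8 | 60.6% | 67.7% | 74.2% |
| 1.0 | 82.3% | 87.0% | 91.5% |

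At dz = 0.8, Holm gives 74.8% at r = 0.3 and 73.1% at r = 0.8. At r = 0.5 the gain of 74.2 − 60.6 = 13.6 points splits into 67.7 − 60.6 = 7.1 from dropping the third pair and 74.2 − 67.7 = 6.5 from Holm.

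**Other measures (dz = 0.8, r = 0.5, in the order of the columns).**
- Both contrasts significant: 43.4%, 51.9%, 65.2%.
- At least one significant: 77.4%, 83.2%, 83.2%. The last two are equal because Holm's first step is Bonferroni over two.
- Only one effect real, power for that one: 60.5%, 67.7%, 67.9%. Holm adds practically nothing here.

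**Error rate.** With no effect at either time, the chance of at least one false claim among the two baseline contrasts is about 3.2% with three-pair Bonferroni and 4.7% with Holm over two (r = 0.5). Over r = 0.3 to 0.7 the ranges are 3.0-3.3% and 4.4-4.8%. All lie under 5%.

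**Intervals under the present text.** An unadjusted 95% interval is 1 − 2.160/2.746 = 21% narrower than the one matching a three-pair test, and 1 − 2.160/2.533 = 15% narrower than the one matching a two-contrast test. It can exclude zero while the adjusted p-value exceeds 0.05.

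**Intervals under Holm.** A contrast significant only at Holm's second step (p between 0.025 and 0.05) has a 97.5% interval that includes zero. The frequency is the difference between Holm and two-contrast Bonferroni in the chance that both are significant: 65.2 − 51.9 = 13.3% of trials at r = 0.5, and 67.5 − 55.6 = 11.9% at r = 0.7. With equal effects, Holm's per-contrast gain over Bonferroni is half of this (13.3/2 ≈ 6.6 points). The extra power comes from exactly the cases in which test and interval disagree.

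**The case against.** The strongest reply is that the SAP nowhere says the correction covers three pairs. The only differences it names are from baseline, so a family of two fits the wording at least as well. This stands. A reader might infer that the plan does spend alpha on 30 v 90 min, but the text supports only that it might, because the family is unstated.

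Three further points stand:
- **Error rate.** Two contrasts with Holm keep the same nominal 5% bound, not the same realised error. Part of the power is bought by the rise from about 3.2% to 4.7%.
- **Intervals.** Bonferroni has exactly matching intervals and Holm does not, which is a fair reason to keep Bonferroni in a plan that promises intervals. The word corresponding in 10.5.1 may also mean adjusted intervals, in which case the present plan has no mismatch.
- **Model.** The figures use separate paired t tests. With the pooled error of a repeated-measures ANOVA, (14 − 1) × (3 − 1) = 26 df, the critical values would be 2.056 at 0.05 and 2.559 at 0.0167. The percentages would change; the ordering of the methods would not.

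A reader might also infer that p-value and interval could point in opposite directions. They share one estimate and one sign, so they can differ only on whether zero is excluded.

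That the study is exploratory and Bonferroni is valid limits the weight of the point. It does not remove the need to say which comparisons are corrected.

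**Conclusion.** The point holds as one of specification and efficiency, not validity. The comparison family, alpha and interval level are unstated for a three-level factor from which only two differences are to be reported.

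If the family is all three pairs, naming the two baseline contrasts and using Holm raises power per contrast from about 61% to 73-75% at an assumed dz of 0.8 at both times. The gain at r = 0.5 is about 10 points at dz 0.5 and 9 at dz 1.0. If the family is already two, the gain at dz 0.8 is about 6-7 points when both effects are real and practically none when only one is.

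The sizes rest on the assumed effects and correlations, equal effects at the two times and paired t tests on 13 df. The ordering does not: Holm over two rejects whenever single-step Bonferroni over two or three does.

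The point concerns time points within one endpoint only. It says nothing about multiplicity across the four agents and C2/C5.

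**What to change.** In 10.5.1 and 10.5.2, replace the Bonferroni post hoc wording with text to this effect: *Within each endpoint, the family consists of two planned contrasts, 30 min v baseline and 90 min v baseline, tested with Holm at two-sided 5%. The 30 v 90 min difference is descriptive.* If exactly matching intervals are wanted, use Bonferroni over the two contrasts instead, at 0.025 each. That still removes the third pair.

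State the interval level: 97.5% per contrast (simultaneous 95%), or 95% labelled as unadjusted. With Holm, add that p-values and 97.5% intervals can disagree on significance. State in the model sentence that baseline is one of the levels.

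No new data or subjects are needed, only SAP wording. The statistical cost is that Holm has no simple matching interval and that realised error moves closer to 5%. There is also a cost of timing: the SAP describes enrolment and dosing of an open-label study in the past tense, and 9.1 treats as a priori only what is defined before database lock. The change should be dated before lock; after it, the result would have to be labelled post hoc. Any correction across agents and C2/C5 would come on top.

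### The repeated-measures ANOVA in SAP 10.5.1 and 10.5.2, run in its usual form, cannot use every available value from a FAS that needs only one post-dose observation

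*SAP*

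**What the plan says.** Section 10.5.1 states that "the treatment comparison will be performed using an ANOVA repeated measures model with Bonferroni corrected post hoc measurements". The next sentence sets the data: "The ANOVA model will use all available data at 30 min and 90 min post dose with LN C2 and LNC5 as dependent variables", with time point as the only factor. Differences from baseline with 95% CIs and p-values are then to be reported.

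Section 10.5.2 names a "one way ANOVA for repeated measures model with Bonferroni corrected post hoc measurements" for the VAS scores and makes the same statement about the data used. The same section assigns a mixed linear model to the post-recovery change in C2 and C5, and to nothing else.

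Section 10.5 fixes the analysis set: "All efficacy analyses will be based on FAS set". Section 7.1 defines it: "All subjects who have taken at least 1 dose of study medication and provided at least 1 post-dose primary endpoint observation". Section 5.3.1 gives the time points as "across three time points (at baseline, 30 min, and 90 min post-dose". On software, section 9.0 says only that the analyses "will be conducted using SPSS (version.22) and Excel".

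**The concern.** A repeated-measures ANOVA in its usual form needs a value at every level of the time factor. A subject with baseline and 30-min values but no 90-min value belongs to the FAS, yet would be removed from that endpoint's model together with the valid 30-min value. The set analysed would then be a completers subset that the plan does not declare. It could also differ between the eight C2 and C5 endpoints (four agents, two thresholds) and the two VAS scores.

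Two things are at stake. The first is precision in a study of 14 subjects, mainly for the 30-min comparison. The second is reproducibility: two analysts following the same text could analyse different subjects.

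**Working it through.** **1. The statements side by side.** Take one FAS subject with baseline and 30-min LN C5 for capsaicin but no 90-min value.

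- Section 7.1: in the FAS, having at least one post-dose primary observation.
- Section 10.5: the FAS is the set for efficacy.
- Section 10.5.1, data sentence: the 30-min value is to be used.
- Section 10.5.1, model sentence, usual form: the subject is dropped from that endpoint.

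The first three and the fourth cannot all be met.

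**2. Does the ANOVA lose subjects in practice?** A simulated 14 x 3 data set had two 90-min values removed (in Python, not SPSS). The repeated-measures ANOVA routine rejected the incomplete data as unbalanced. After deletion of incomplete subjects it used 12 subjects and 36 observations, and the error degrees of freedom, (3-1)(n-1), fell from 2 x 13 = 26 to 2 x 11 = 22. A random-intercept mixed model used all 14 subjects and 42 - 2 = 40 observations.

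**3. Size.** The plan has no figure of its own to reproduce: section 9.3 gives no power, effect size or SD, and no missing rate appears anywhere. Inputs:

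- n = 14 (sections 3.0 and 9.3).
- Three time points (section 5.3.1).
- Assumed: k = 2 or 4 subjects lack only the 90-min value.
- Assumed: known compound-symmetric covariance with correlation r from 0.3 to 0.9.

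Standard errors below are relative to 14 complete subjects.

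*Complete cases, either contrast:* ratio = sqrt(14/(14-k)).
- k = 2: sqrt(14/12) = 1.080
- k = 4: sqrt(14/10) = 1.183

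*Mixed model, 30 min versus baseline:* both values are present in all 14 subjects, so the ratio is 1.000.

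*Mixed model, 90 min versus baseline:* ratio = sqrt(1 + [(1+2r)/(2(1+r))] x [14/(14-k) - 1]).
- The bracket in r is 1.6/2.6 = 0.615 at r = 0.3 and 2.8/3.8 = 0.737 at r = 0.9.
- k = 2: sqrt(1 + 0.615 x 0.1667) = 1.050, and sqrt(1 + 0.737 x 0.1667) = 1.060
- k = 4: sqrt(1 + 0.615 x 0.4) = 1.116, and sqrt(1 + 0.737 x 0.4) = 1.138

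| Missing at 90 min | Contrast with baseline | Rise in SE, complete cases | Rise in SE, mixed model |
|---|---|---|---|
| 2 of 14 | 30 min | 8% | 0% |
| 2 of 14 | 90 min | 8% | 5-6% |
| 4 of 14 | 30 min | 18% | 0% |
| 4 of 14 | 90 min | 18% | 12-14% |

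The avoidable loss falls mainly on the 30-min contrast. Most of the 90-min loss comes from the missing values themselves.

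**4. How easily the conflict arises.** Assume that each post-dose value of an endpoint is missing with probability m, independently at 30 and 90 min, with baseline complete. Given 14 subjects with at least one post-dose value, the chance that at least one is dropped is 1 - [(1-m)^2/(1-m^2)]^14. This is 43%, 75%, 94% and 99% at m = 2%, 5%, 10% and 15%. These rates are illustrative only.

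**The case against.** The strongest reply is that the SAP never prescribes a complete-case analysis. It does not call the ANOVA classical and names no SPSS procedure, and its one explicit statement on inclusion is that available data are used. That stands as far as it goes: the reading rests on the model's name and on the separate naming of a mixed linear model in section 10.5.2. If a mixed-model fit was intended throughout, the text still has to say so.

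Other objections also carry weight:

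- FAS membership depends on any one post-dose primary observation across eight endpoints. It does not by itself promise that every member enters every model. The conflict comes from FAS membership together with the data sentence.
- Gaps may be few. Baseline and both post-dose series fall on one day, dosing is single, and section 9.2 imputes an unreached C5.
- A reader might infer that baseline is left out of the model, because the data sentence names only 30 and 90 min. Sections 5.3.1 and 10.5.1 largely settle this: they list three time points and call for differences from baseline. It is loose wording.
- A reader might add that the F-test's sphericity assumption is not addressed. That is a weak argument here. Sphericity concerns the omnibus test, pairwise contrasts using their own difference variances do not need it, and a compound-symmetric mixed model assumes more.
- A mixed model is not free of bias. It relies on missing at random, and if absence depends on the unseen cough response it is biased too.

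**Conclusion.** The point holds as an internal conflict: the named model, the data sentence and the FAS definition cannot all be honoured if any value is missing. If the data are complete, nothing is lost numerically.

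With 2 to 4 of 14 subjects lacking only the 90-min value, the avoidable rise in standard error is 8 to 18 percentage points for the 30-min contrast and about 2 to 7 for the 90-min contrast (for example 1.080 - 1.060 and 1.183 - 1.116). This rests on the assumed missing pattern and on a known compound-symmetric covariance.

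Two stronger readings are not supported. One is that the whole loss from 14 to 12 or 10 complete subjects could be avoided; most of the 90-min loss cannot be recovered by any model. The other is that the ANOVA necessarily biases the result; the SAP gives no missing rate or mechanism from which to conclude that. The matter should be corrected before database lock, but it does not invalidate the study.

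**What to change.** In sections 10.5.1 and 10.5.2, replace the repeated-measures ANOVA with a linear mixed model fitted to all FAS observations of LN C2, LN C5 and each VAS score:

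- time (baseline, 30 min, 90 min) as a categorical fixed effect, with baseline named as a level;
- subject as the repeated unit, with one pre-stated covariance structure;
- small-sample degrees of freedom, for example Satterthwaite;
- Bonferroni-adjusted contrasts of 30 min and 90 min against baseline, with CIs adjusted to match.

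The cost is SAP wording and a different fitting procedure; the SAP already plans a mixed model for the recovery analysis. With complete data and compound symmetry the model reproduces the ANOVA. The downside is small: reliance on missing at random and on the chosen covariance with 14 subjects.

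A lesser alternative is to keep the ANOVA, delete the statement that all available data are used, declare a complete-case analysis and report the number analysed per endpoint. That removes the conflict but not the loss of valid 30-min data.

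Neither option deals with an unreached C2. Section 9.2 has a rule only for C5. An unreached C2 is a censored value and needs its own pre-stated rule.
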